## RESEARCH PROTOCOL

### Purpose and **Specific Aims** of the study

Family caregivers work with hospice teams to help implement the patient's care plan. They spend time tending to the day-to-day needs of the patient, managing and administering medications for comfort, and providing emotional and spiritual support. While many family caregivers find meaning in their role, they are also likely to suffer from depression, anxiety, stress and poor physical health compared to non-caregivers. Therefore, supporting family caregivers is essential both for their well-being as well as the well-being of the patients they care for.

This proposal seeks to develop culturally tailored videos, using experience based codesign (EBCD) methodology, to better communicate with underrepresented (Puerto Rican and African American) family caregivers around symptom related issues at the EoL. African Americans make up the second largest racial group receiving hospice care and Puerto Ricans make up the second largest Hispanic group in the US.

There is a dearth of evidence based educational resources for caregivers. Underrepresented caregivers are less likely to have any culturally tailored resources despite the fact that literature has shown differences in preferences and beliefs among different ethnic and racial groups at the EoL. This is noteworthy given tailored education has shown to be effective in communicating information to improve knowledge and behaviors. This proposal aims to develop culturally tailored educational videos focused on symptom related issues to improve caregivers' comfort in managing these issues, preparedness and self-efficacy, factors which are associated with improved caregiver outcomes.

**Specific Aim 1:** *To gather input, through interviews and focus groups, from Puerto Rican (n=15) and African American (n=15) family caregivers to understand culturally based views and knowledge gaps around symptom related issues in home hospice care.*

**Specific Aim 2:** *To develop 12 video scripts, using experience based codesign, with input from a stakeholder group (e.g., family caregivers, hospice physician/nurse practitioner, nurse, social worker, chaplain). Scripts will be used to produce educational videos on symptom related issues for Puerto Rican and African American caregivers.*

**Specific Aim 3:** *To pilot caregiver educational videos with Puerto Rican (n=10) and African American (n=10) family caregivers receiving home hospice care. Caregivers' comfort in dealing with symptom related issues, level of preparedness and self-efficacy will be assessed, pre and post intervention, along with its perceived usefulness and limitations.*

**Study design**, research methods, proposed intervention(s), rationale, hypotheses to be tested or issues to be addressed

### **Aim 1**

Aim 1 will consist of individual interviews and/or focus groups (dependent on participant preference and availability) conducted with Puerto Rican and African American family caregivers who have been discharged from home hospice care (n=15 for each group). Family caregivers will be recruited from the Visiting Nurse Service of New York (VNSNY) hospice organization, Hospicio Toque de Amor, and Hospicio Luz Celeste.

The research team will work collaboratively with hospice leadership at each site to generate a recurring list of home hospice patients who have been discharged over the prior six months. This list will contain contact information (e.g. name, phone number) of the listed family caregiver along with the name, race/ethnicity and age of the hospice patient for recruitment purposes. In order to be mindful of the sensitive nature recruiting caregivers immediately after a hospice discharge, a research member will wait one month from the care recipient's discharge date before contacting the family caregiver for participation.

Caregivers will be contacted by phone and those who qualify for the study and express interest in participating will be scheduled for either a focus group session or an individual interview, based on caregiver preference and schedule. Both methods will be conducted either virtually using teleconference software or in-person at the participant's residence. Electronic informed consent will be obtained for virtual participation and signed paper informed consent will be obtained for in-person participation prior to enrollment into the study. Demographic data will also be collected from each caregiver participant after enrollment which will include: age, gender, religion, birthplace, education level, relationship to patient, occupation, average number of hours spent caregiving per week when receiving hospice care. We will also contact the collaborating hospices to collect the hospice diagnosis of their care recipients.

An open-ended interview guide will be used. The aims of the interviews/focus groups with family caregivers are: 1) to identify symptom related issues that arise in home hospice care; 2) to assess understanding, knowledge, and culturally based views around these concerns; 3) to brainstorm suggestions on how to convey symptom related issues through storytelling; and 4) to understand what critical cultural factors are important to consider when developing these videos. Interviews and focus groups will be audio recorded and analyzed using qualitative methods. Participants will be compensated with a \$50 gift certificate. After participants have completed the interview/focus group in Aim 1, a member of the research team will ask participants if they would be willing to be contacted to participate in Aim 2 of this study. For those that express interest, the research member will confirm the participant's name and contact info (phone number).

Data collected will be used to help serve as topics for video script development in Aim 2.

### **Aim 2**

Aim 2 will use principles of experience based co-design (EBCD) as part of the study design. EBCD is an approach that engages patients/caregivers and healthcare staff in partnership to develop and improve health services or pathways of care. For this study, the EBCD model will consist of bringing family caregivers and hospice staff together to share in their experiences and work on the study's aim through an iterative process.

Puerto Rican and African American stakeholder group (i.e., caregivers, hospice nurses, nurse practitioners, physicians, social workers, spiritual counselors) will be recruited from VNSNY hospice, Hospicio Toque de Amor, and Hospicio Luz Celeste. The research team will work collaboratively with hospice leadership at each site to identify potential participants for Aim 2. Participants in Aim 1 of the study who express interest in being contacted to participate in Aim 2 will also be recruited. Participants who express interest in participating as a stakeholder member will be contacted by phone or email to schedule a time to meet. These group meetings will be conducted virtually using teleconference software or in-person meeting or a combination of both (some participants being in-person and some using teleconference software). This will be dependent on the preference of the participants and availability of the research staff member conducting the study. Electronic informed consent will be obtained for virtual participation and signed paper informed consent will be obtained for in-person meetings at the time of study enrollment.

Each stakeholder group (i.e., Puerto Rican and African American) will consist of three family caregivers, a physician or nurse practitioner, nurse, social worker, and spiritual counselors. In these meetings, the research team will present to the group the four symptom related issues generated from Aim 1. The group will work collaboratively together and with the research team to create video scripts that incorporate symptom related concerns shared by caregivers with culturally based views, practices, and beliefs. Each member of the group will play a critical role in bringing their own experiences and perspective to help shape the content of the video scripts. The goal of the meetings will be to create tailored messaging that aims to enhance understanding and knowledge for Puerto Rican and African American caregivers.

This process will be iterative, as each stakeholder group will meet with the research team on multiple occasions to create and refine drafts of each script. Participants will be compensated with a \$50 gift certificate for each session they participate. During this process, relevant cultural components will be discussed and incorporated. These components include: visual presentation (e.g., actors/actresses, set development), language and tone, body language, family dynamics and religion/spirituality. After the completion of these meetings, a total of 12 video scripts will be developed for Puerto Rican (4 English versions, 4 Spanish versions) and African American (4 versions) caregivers. These video scripts will then be produced in collaboration with Maestro films, a film production company.

### **Aim 3**

Aim 3 will be a cross-sectional study conducted with VNSNY hospice, Hospicio Toque de Amor, and Hospicio Luz Celeste. Names of Puerto Rican and African American caregivers receiving home hospice care will be referred to the study team by the site leader/hospice leadership at each hospice. A research member will contact potential participants by phone or email to inform them about the study. Those who express interest will be asked to schedule a time to meet virtually through video conference where electronic informed consent will be obtained or in-person where paper informed consent will be obtained.

Demographic data will be collected from each caregiver participant which will include: age, gender, religion, birthplace, education level, relationship to patient, occupation, average number of hours spent caregiving per week. Prior to showing participants the culturally tailored videos, a research member will administer a set of Likert style questions developed by the research team around comfort in managing symptom related issues. The same questions will be administered again post video intervention. In addition, the preparedness scale and the caregiving competence scale will be administered to participants pre and post video intervention. The PI will not be involved in the administering the intervention for this study.

After the culturally tailored videos have been shown to the participant, a research member will also conduct an open-ended interview about content, reactions, attitudes, usefulness and limitations around each video. Interviews will be conducted in either English and/or Spanish. Participants' responses will be audio recorded and analyzed using qualitative methods. Participants will be compensated with a \$50 gift certificate.

**Sample selection/ Data sources.** Describe characteristics of the subject population, such as their anticipated number, age, sex, ethnic background, and state of health. Identify criteria for inclusion or exclusion. If excluding certain racial or ethnic groups, please explain rationale and how exclusion may limit generalizability of findings. Explain the rationale for use of special classes of vulnerable subjects, such as pregnant women, children, mentally impaired, especially those whose ability to give voluntary informed consent may be in question. If vulnerable populations are to be used, investigators must deal thoroughly with the potential risk. If you need access to HIPAA-defined protected health information (*PHI*-see attached list) in order to screen for potential participation, for secondary data analysis or for other purposes and you do not plan to get authorization for access to this data from each individual you must request a *waiver of authorization* (see instructions below).

### **Aim 1**

Criteria for caregiver participation include:

- Family caregivers who identify themselves as African American (N=15) or Puerto Rican (N=15)
- English and/or Spanish speaking
- 18 year of age or older
- Family caregiver whose care recipient was 65 years or older when receiving hospice care and has been discharged from home hospice services within the past 6 months (This is a NIA funded study so age criteria for care recipient was included)
- Participants will need to have access to internet and a computer/tablet in order to be able to sign an electronic consent form and participate in the interview/focus group (if they elect to participate virtually).
- Participants will be excluded if they are unable to use technology to access the electronic consent form and/or virtual interview/focus group (if they elect to participate virtually).

### **Aim 2**

Criteria for caregiver participation include:

- Family caregivers who identify themselves as African American (N=3) or Puerto Rican (N=3)
- English and/or Spanish speaking
- 18 year of age or older
- Family caregiver whose care recipient was 65 years or older when receiving hospice care and has been discharged from home hospice services within the past 6 months
- Caregivers who participate in Aim 1 can be recruited to participate in Aim 2 of the study if they are agreeable to being contacted after completing Aim 1.
- Participants will need to have access to internet and a computer/tablet in order to be able to sign an electronic consent form and participate in the interview/focus group. (If focus groups are held virtually)
- Participants will be excluded if they are unable to use technology to access the electronic consent form and/or virtual working group. (If focus groups are held virtually)

Criteria for hospice staff participation include:

- A VNSNY, Hospicio Toque de Amor, or Hospicio Luz Celeste hospice staff member who is a physician, nurse practitioner, nurse, social worker, or chaplain.
- Staff who identify themselves as Puerto Rican (N=4) or African American (N=4)
- Staff who have provided hospice care to Puerto Rican and/or African American patients
- English and/or Spanish speaking.
- Participants will need to have access to internet and a computer/tablet in order to be able to sign an electronic consent form and participate (If focus groups are held virtually)
- Participants will be excluded if they are unable to use technology to access the electronic consent form and/or virtual working group (If focus groups are held virtually)

### **Aim 3**

Criteria for caregiver participation include:

- Family caregivers who identify themselves as Puerto Rican (N=10) or African American (N=10)
- English and/or Spanish speaking
- 18 year of age or older
- Currently receiving home hospice services with a patient who is 65 years or older

- Participants who prefer to conduct the study virtually will need to have access to internet and a computer/tablet in order to be able to sign an electronic consent form and participate in the pilot intervention.

\*\*Our rationale for only including participants who identify as Puerto Rican or African American is based on the aims of the grant to develop culturally tailored videos. We understand that this will not be generalizable to other caregiver populations of different race/ethnicity.

**Procedures for recruiting study subjects.** Describe how potential study subjects will be approached. The protocol needs to include any telephone scripts or letters to be used for recruitment purposes, and incentives used to solicit participation.

### **Aim 1**

Hospice site leaders will generate a list of names of home hospice patients and their caregivers who have been discharged over the prior six months. Site leaders will then reach out to caregivers to obtain permission to release their names and contact information to Drs. [name] and [name]. This revised list will contain contact information (e.g. name, phone number) of the listed family caregiver along with the name, race/ethnicity and age of the hospice patient for recruitment purposes. Each site leader will transfer this list to Drs. [name] and [name] via encrypted email.

Caregivers will be contacted (see phone script for Aim 1 below) by the study team and those who meet study criteria and express interest in participating will be scheduled for either a focus group session or an individual interview, based on preference and scheduling. Both methods will be conducted either virtually using teleconference software (e.g., Zoom) or in-person.

[name], [name], or [name] will conduct virtual (Zoom) interviews for Aim 1. For participants recruited at VNSNY who request an in-person interview, [name] or [name] will conduct these interviews. For participants recruited at Hospicio Toque de Amor or Hospicio Luz Celeste who request an in-person interview, [name] will bundle those requests together and fly down to Puerto Rico to conduct those interviews.

Informed consent will be obtained prior to enrollment into the study (electronic or paper). Electronic informed consent will be obtained through DocuSign which is HIPAA compliant and have electronic signature capabilities. Participants will be compensated with a \$50 gift certificate.

### **Aim 2**

Hospice site leaders will generate a list of names of home hospice patients and their caregivers who have been discharged over the prior six months. Site leaders will then reach out to caregivers to obtain permission to release their names and contact information to Drs. [name] and [name]. This revised list will contain contact information (e.g. name, phone number) of the listed family caregiver along with the name, race/ethnicity and age of the hospice patient for recruitment purposes. Each site leader will transfer this list to Drs. [name] and [name] via encrypted email. The study team will also reach out to the pool of caregivers who participated in Aim 1 and expressed interest in being contacted to participate in Aim 2 of the study.

Caregivers will be contacted by phone (see phone script for Aim 2 below) and those who express interest in participating will be scheduled for a stakeholder group meeting using teleconference software or in-person.

Contact information for hospice staff (i.e., physician or nurse practitioner, nurse, social worker, and chaplain) will be provided by hospice leadership or site leaders and an invitation to participate will be sent by email (see email script below). Those who express interest in participating will be scheduled for a stakeholder group meeting.

Participants in the Puerto Rican stakeholder group will be given the option of conducting an in-person meeting at the offices of Hospicio Luz Celeste. Participants in the African American stakeholder group will be given the option of conducting an in-person meeting at the offices of the Division of Geriatrics and Palliative Medicine at Weill Cornell Medicine. Both in-person sites will also have teleconference capabilities if a portion of participants in the stakeholder group prefer to participate via teleconference.

A member of the research team ([name], [name], [name], or [name]) will guide the African American stakeholder group meeting. [name] will guide the Puerto Rican stakeholder group meeting. African American and Puerto Rican group meetings will be held separately. Stakeholder group meetings will be held iteratively (e.g., weekly) for up to 4 weeks to develop and refine 12 video scripts. Informed consent will be obtained prior to enrollment into the study (electronic or paper). Electronic informed consent will be obtained through DocuSign which is HIPAA compliant and have electronic signature capabilities. Participants will be compensated with a \$50 gift certificate for each stakeholder meeting they attend.

### **Aim 3**

Hospice site leaders will generate a weekly list of names of home hospice patients and their caregivers who are currently receiving home hospice care. Site leaders will then reach out to caregivers to obtain permission to release their names and contact information to Drs. [name] and [name]. This revised list will contain contact information (e.g. name, phone number) of the listed family caregiver along with the name, race/ethnicity and age of the hospice patient for recruitment purposes. Each site leader will transfer this list to Drs. [name] and [name] via encrypted email.

A research member will contact potential participants by phone to informed them about the study (see phone script for Aim 3 below). Those who express interest will be asked to schedule a time to meet virtually through video conference or in-person. For participants who elect to meet virtually, electronic informed consent will be obtained through DocuSign which is HIPAA compliant and have electronic signature capabilities.

[name], [name], [name] or [name] will conduct virtual visits for Aim 3. For participants who request an in-person visit, [name] or [name] will conduct in-person visits for participants at VNSNY. [name] will schedule in-person visits for participants at Hospicio Toque de Amor and Hospicio Luz Celeste based on her availability. She will bundle those requests together and fly down to Puerto Rico to conduct research activities needed for Aim 3. Participants will be compensated with a \$50 gift certificate.

No external investigators (unless they are a VNSNY employee or VNSNY volunteer/intern) will be given names or contact information until subject approval is obtained through a VNSNY provider (for subjects being recruited at VNSNY). For subjects being recruited at Hospicio Toque de Amor, or Hospicio Luz Celeste, no external investigators will be given contact information unless subjects approval is obtained by the site leader at that institution.

**Consent forms and additional PHI authorizations.** A person *consents to participate in research and authorizes use and disclosure of protected health information*. Consent forms should be clear, easy to understand, and written at a recommended fifth grade reading level. If children under 18 years of age will be included in the study, then parental consent may also be required. If consent forms are not deemed necessary, the rationale for this should be included in the statement of protection of human subjects in the proposal body. The investigator is responsible for retaining signed consents in the research files. Because a consent form documents an agreement between two parties, the subject should be given a copy to keep as well. *A list of elements required in an informed consent form & language for broad consent are attached along with a prototype consent form.* If protected health information (PHI) will be recorded for patients consenting to research then additional elements need to be included in the consent or a separate authorization is required. Minimal requirements for an authorization form are on page 6 of this application packet.

## **Brief overview of analytic methods.**

Audio recordings from interviews/focus groups will be transcribed verbatim. Content analysis, a method for classifying verbal and behavioral data into categories of similar meaning, will be used to analyze data. A deductive approach will be implemented. During open coding, short sections of text representing discrete concepts will be identified from transcripts and tagged with a code. This will be followed by focused coding, which involves comparing codes within and across interviews. Lastly, axial coding, where codes are compared between transcripts in order to develop a set of categories and/or themes, will be the third step of the coding process. A code book will be developed to systematize data analysis and ensure findings are reproducible. Interrater reliability and trustworthiness will be evaluated as part of the qualitative analytic process.

Two individuals with varied backgrounds will independently review and code the transcripts. Discrepancies will be resolved through discussion until consensus is reached.

Quantitative outcomes being measured include preparedness for caregiving scale, chronic pain self-efficacy scale, caregiver competence scale and caregiver comfort in managing symptom related issues. These scales/survey questions will be administered pre and post video intervention. Using the preparedness for caregiving scale as one of the primary outcomes with the assumption of a 25% improvement in scores based on a mean of 16 and SD of 6.8, there will be 80% power to detect an effect size of  $d=0.58$ , which is considered a moderate effect.

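### The 80% power at d=0.58 matches all 20 caregivers with an undeclared one-sided test; a two-sided 5% paired test has about 69%

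*Combined protocol and SAP*

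**What the plan says.** The power statement is one sentence in *Brief overview of analytic methods*. It begins "Using the preparedness for caregiving scale as one of the primary outcomes", continues "with the assumption of a 25% improvement in scores based on a mean of 16 and SD of 6.8", and concludes that "there will be 80% power to detect an effect size of" d=0.58, which it describes as moderate. The sentence before it describes how the outcomes are collected: "These scales/survey questions will be administered pre and post video intervention".

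The sample size is given elsewhere. The Aim 3 eligibility criteria list "Family caregivers who identify themselves as Puerto Rican (N=10) or African American (N=10"), so 20 in all. Under Aim 2 the scripts are written separately for "Puerto Rican (4 English versions, 4 Spanish versions) and African American (4 versions) caregivers".

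The document does not name a statistical test for the scales. It also gives no significance level, sidedness, pre-post correlation or allowance for dropout, and does not say whether the two groups are pooled. The SD of 6.8 stands beside a mean score and is not described as an SD of change.

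**The concern.** A power figure can be interpreted only with its sample size, test, error rate and variance assumption, and this one has none of them attached. A reader will supply the usual default, a two-sided 5% test on paired data. If 80% holds only under a different, undeclared choice, that reader will think the pilot more sensitive than it is.

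Two things depend on this. The smallest change that the pilot can reliably detect on a scale the plan treats as primary would be understated. The choice between a one-sided and a two-sided test would also remain open until the data are seen, because nothing in the plan fixes it.

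**Working it through.** **Inputs from the documents.** Mean 16, SD 6.8, improvement 25%, d=0.58 and power 80% (*Brief overview of analytic methods*); 10 + 10 = 20 caregivers (Aim 3 criteria); each caregiver measured before and after the videos.

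**Assumptions, because the documents are silent.** Significance level 5%; a paired t-test; no dropout; to begin with, d is the mean change divided by the SD of change.

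**Step 1: the effect size.** 25% × 16 = 4 points, and 4 / 6.8 = 0.588. The plan prints 0.58; the difference is immaterial.

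**Step 2: reproduce the 80%.** For a paired t-test on n people, the statistic has a noncentral t distribution with n − 1 degrees of freedom and noncentrality d × √n. For n=20 and d=0.58 the noncentrality is 0.58 × √20 = 2.594, with 19 degrees of freedom.

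| Test, n=20 | Critical t | Power at d=0.58 | Power at d=0.588 | d detectable with 80% power |
|---|---|---|---|---|
| One-sided 5% | 1.729 | 80.4% | 81.3% | 0.577 |
| Two-sided 5% | 2.093 | 69.2% | 70.4% | 0.660 |

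The one-sided detectable effect, 0.577, rounds to the printed 0.58. So the plan's figure matches a pooled, one-sided 5% paired t-test. A two-sided 10% test gives the same 80.4%.

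**Step 3: the two-sided reading in points.** If 6.8 is the SD of change, 0.660 × 6.8 = 4.5 points, or 4.5 / 16 = 28% of the mean, against the 4 points (25%) assumed. Two-sided 80% power at d=0.58 would take 26 pairs.

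**Step 4: if 6.8 is the SD of scores.** With equal SDs before and after and pre-post correlation r, the SD of change is 6.8 × √(2(1 − r)). The standardized change for a 4-point gain is then 0.588 / √(2(1 − r)). With n=20 and a two-sided 5% test:

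| r | SD of change | Standardized change | Power |
|---|---|---|---|
| 0.3 | 8.05 | 0.497 | 56% |
| 0.5 | 6.80 | 0.588 | 70% |
| 0.7 | 5.27 | 0.759 | 90% |

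Power passes 80% just above r = 0.60. At r = 0.5 the SD of change equals the SD of scores, so using 6.8 directly in a paired test amounts to assuming that correlation.

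**Step 5: each group of 10, for context.** At d=0.58, power is 37% two-sided and 52% one-sided. The 95% confidence interval for mean change has half-width 2.262 × 6.8 / √10 = 4.9 points, if the SD of change is 6.8.

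**The case against.** The strongest reply is that nothing has been miscalculated. The figure reproduces at n=20, which is the Aim 3 total, and the printed effect size is what a one-sided 5% paired test gives. On this view the fault is incomplete reporting in a small pilot that has no decision rule tied to significance. That stands: the 80% is not an arithmetic error.

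The reply also holds that a two-sided shortfall is not inevitable. This stands too. If 6.8 is the SD of scores and the pre-post correlation is above about 0.60, a pooled two-sided test does reach 80% for 4 points. It does not rescue the sentence, because the plan states no correlation and at 0.3 the power would be 56%.

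A reader might infer that the plan promises 80% power for each group of 10, since the groups watch separately written videos, and that the 37% shows the claim to be false. The documents do not support that. The power sentence names no group, no group-specific test is planned, and the match at n=20 points to pooling. The 37% is context for how the group results should be read.

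A reader might also take "Aim 3 will be a cross-sectional study" to mean that the pre and post data are unpaired. The same section has the same questions put to each participant before and after the videos, so the label is a clerical slip and does not bear on the power.

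**Conclusion.** The 80% can be reconstructed for the pooled 20 caregivers, but the match found rests on an undeclared one-sided 5% test (equivalently, a two-sided 10% test). Under a two-sided 5% paired t-test the power at d=0.58 is 69%, and 80% is reached at about d=0.66. These figures assume no dropout and that d is standardized by the SD of change. If 6.8 is the SD of scores, two-sided power for 4 points ranges from about 56% to 90% over correlations of 0.3 to 0.7, and the documents give no basis for choosing within that range. The point should be corrected because a stated operating characteristic cannot be relied on as printed. The design itself need not change.

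**What to change.** Replace the power sentence in *Brief overview of analytic methods* with wording such as:

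> With 20 caregivers pooled, a two-sided 5% paired t-test has 80% power for a mean change of 0.66 SD of the change score, and 69% at d=0.58, taking 6.8 as the SD of change (pre-post correlation 0.5 if 6.8 is the SD of scores).

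If the investigators intend a one-sided test, they should say so, justify it, and print the two-sided figure beside it.

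Add that the pooled pre-post change is the powered analysis and that changes in each group of 10 will be reported descriptively with 95% confidence intervals. In the same edit, describe Aim 3 as a single-group pre-post study.

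The cost is wording only, with no added enrolment, visits or measurements. The stated detectable effect becomes less favourable, 0.66 instead of 0.58.
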